9.3.2.2 Best Overall Response Rate (BORR)

BORR is defined by population subset as the total number of treated subjects in the subset whose BOR is CR or PR, divided by the total number of treated subjects in the subset.

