9.2 Populations for Analyses

- Enrolled Subjects: All subjects who signed and informed consent form and were registered.
- Treated Subjects (Safety Population): Includes all subjects in the study who receive at least one dose of ipilimumab. Unless otherwise indicated, analyses of drug exposure and safety will be performed on this population as treated.

- Evaluable Subjects: Includes all subjects who received at least 1 dose of ipilimumab and the full WBRT therapy.
- Biomarker Subjects: Includes all treated subjects with at least baseline biomarker studies.

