9.3.2.3 Disease Control Rate (DCR)

DCR is as the total number of treated subjects in each population subset with BOR of CR, PR or SD, divided by the total number of treated subjects in the subset.

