1.5.3. BEST RESPONSE (Evaluable)

Following the protocol, for the efficacy analysis the population of was used evaluable patients: $n = X$ (see section 1.1)

Table 34. Best response (Evaluable)

		N (%; 95% CI)
Best response (Criteria modified from WHO)	CR	
	PR	
	EE	
	PE	
	NE (Not evaluated)	
	Total	
Best response (Response Criteria related to immunity. CRri)	RCri	
	RPri	
	EEri	
	PEri	
	NEri (Not evaluated)	
	Total	

According to protocol: Overall best response rate (TMRG)

The MRG is defined by a population subgroup as the total number of patients treated in the subgroup whose MRG is CR or PR, divided by the total number of patients treated in the subgroup.

Table 35. TMRG (Evaluables)

		N (%; 95% CI)
TMRG: CR or PR (Modified WHO Criteria)	No	
	Yes	
	Not evaluated	
	Total	
TMRG: CR or PR (Response Criteria related to immunity. CRri)	No	
	Yes	
	Not evaluated	
	Total	

According to protocol: Disease control rate (TBI)

TBI is defined as the total number of patients treated in each subgroup whose GRM is CR, PR or EE, divided by the total number of patients treated in the subgroup.

Table 36. TBI (Evaluable)

		N (%; 95% CI)
TCE: CR or PR or EE (Modified WHO Criteria)	No	
	Yes	
	Not evaluated	
	Total	
TCE: CR or PR or EE (Response Criteria related to immunity. CRri)	No	
	Yes	
	Not evaluated	
	Total	

Table 37. Time to best response (evaluable)

	N ¹	Mean (SD)	Median (Min-Max)
Time to best WHO response (months from 1st cycle of ipilimumab)			
Time to best response CRri (months from 1st cycle of ipilimumab)			

1: Patients with response recorded in CRDe

Table 38. Time to best response (Evaluable) according to MRG

Time to best response	N ¹	Mean (SD)	Median (Min-Max)
Best global response (modified WHO criteria)	CR		
	PR		
	EE		
	PE		
Time to best response	N ¹	Mean (SD)	Median (Min-Max)
Best Overall response (Response Criteria related to immunity. CRri)	RCri		
	RPri		
	EEri		
	PEri		

1: Patients with response recorded in CRDe

According to protocol: Duration of response

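### The protocol defines BORR and DCR over all treated patients, but the SAP tabulates both only on the evaluable set, which likely biases them upward

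*Protocol*

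**What the plan says.** Protocol section 9.2 defines two nested sets. The treated set: "Includes all subjects in the study who receive at least one dose of ipilimumab". The evaluable set: "Includes all subjects who received at least 1 dose of ipilimumab and the full WBRT therapy". It assigns exposure and safety to the treated set and assigns no response endpoint to the evaluable set. Among the protocol's efficacy rules, only the sample-size section (9.1) uses evaluable patients, for 1-year survival.

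Protocol section 9.3.2.2 gives BORR as the number of treated subjects with a complete or partial best response, "divided by the total number of treated subjects in the subset". Section 9.3.2.3 gives DCR as the number of treated subjects "with BOR of CR, PR or SD, divided by the total number of treated subjects in the subset".

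SAP section 1.5.3 says that, following the protocol, "for the efficacy analysis the population of was used evaluable patients". It then repeats the BORR definition as the number of patients "whose MRG is CR or PR, divided by the total number of patients treated in the subgroup", and does the same for DCR. Tables 34 to 36, which carry these results, are all labelled as evaluable. The SAP has no response table for treated patients.

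**The concern.** The SAP's response tables depart from the protocol's definition and from the definition the SAP itself prints above them. The departure is unlikely to be neutral. Membership of the evaluable set depends on something that happens after the first dose, namely completing WBRT, and a patient must live long enough to do that. Early deaths are failures for response and for disease control, and this set removes them. In a single-arm trial there is no control group subject to the same selection, so any bias passes straight into the reported rate and into comparisons with other series.

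**Working it through.** **The plan's own figures.** The documents give no target, sample size or power for BORR or DCR, so there is no figure for these endpoints to reproduce. The one design calculation, for 1-year survival, does reproduce: with 56 evaluable patients and success at 17 or more, exact binomial tails give a one-sided alpha of 0.0432 at 20% and a power of 0.806 at 35%. It does not bear on the response denominators.

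**Step 1: who can be treated but not evaluable.** Anyone with at least one ipilimumab dose who does not complete WBRT. SAP Table 14 has rows for premature end of radiotherapy and its reasons, so such patients are foreseen.

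**Step 2: how they count under the protocol's definition.**
- The first scheduled scan after baseline is at week 12 (protocol 6.4.2).
- A best response of stable disease needs an assessment of stable disease, or an unconfirmed response, at week 12 (protocol 6.4.2.g).
- A complete or partial response must be confirmed at least 4 weeks after it is first seen (same section).

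WBRT starts between C1D2 and C2D1 (synopsis) and runs for 10 daily fractions (protocol 5.2). It therefore ends about 2 weeks after the first dose at the earliest and about 5 weeks at the latest start. A patient who dies before that cannot have stable disease and practically cannot have a confirmed response. Such a patient is a failure for both BORR and DCR.

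A patient who stops WBRT for another reason and is later scanned may be a success or a failure. Protocol section 3 asks for a 12-week tumor assessment in everyone who enters treatment, so these outcomes should be available.

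**Step 3: size under a stated model.** Assumptions: exponential survival, 1-year survival S of 20% or 35% (the two rates in protocol 9.1), and exclusions that are only deaths before WBRT completion at day t.

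Proportion excluded = 1 − S^(t/365.25). Multiplier on either rate = 1/(1 − proportion excluded).

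| t | S | Excluded | Multiplier |
|---|---|---|---|
| 14 days (start C1D2) | 35% | 3.9% | 1.04 |
| 14 days (start C1D2) | 20% | 6.0% | 1.06 |
| 35 days (start C2D1) | 35% | 9.6% | 1.11 |
| 35 days (start C2D1) | 20% | 14.3% | 1.17 |

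If every treated patient completes WBRT, the multiplier is 1.00.

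**Step 4: the same effect in patient counts.** Assume 56 evaluable patients (the planned number), between 56 and 66 treated (66 is the synopsis figure for patients included), and no success among those left out. The counts of 11 responders and 28 patients with disease control are illustrative.

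| Treated | BORR, 11 responders | DCR, 28 controlled | Evaluable/treated ratio of rates |
|---|---|---|---|
| 56 | 11/56 = 19.6% | 28/56 = 50.0% | 1.00 |
| 58 | 11/58 = 19.0% | 28/58 = 48.3% | 58/56 = 1.036 |
| 60 | 11/60 = 18.3% | 28/60 = 46.7% | 60/56 = 1.071 |
| 66 | 11/66 = 16.7% | 28/66 = 42.4% | 66/56 = 1.179 |

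**Step 5: when the direction would reverse.** With 66 treated and 56 evaluable, the two BORRs are equal if the 10 patients left out include 10 × 11/56 = 1.96 responders. For DCR the break-even is 10 × 28/56 = 5. Below these counts the evaluable rate is too high; above them it is too low.

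**The case against.** **The protocol's wording may allow it.** BORR and DCR are defined within a population subset, a term the protocol does not define. Every evaluable patient is also treated, so treated subjects in the subset could be read as the evaluable set. Protocol 9.2 reserves the treated set only for exposure and safety, and 9.1 uses evaluable patients for the primary endpoint. This reading is possible but strained: treated subjects have their own definition in 9.2, and nothing links response to the evaluable set. If the sponsor did mean the evaluable set, the text still needs correcting, because the SAP prints one denominator and uses another.

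**The SAP's own population definition cannot be checked.** The SAP refers to its section 1.1 for the evaluable population, and that section is not in the text available. The requirement of full WBRT is therefore taken from the protocol. This caveat stands.

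**Stronger readings that the documents do not support.** A reader might infer that both rates are certainly inflated. That depends on the number and outcomes of the patients left out, which are not given. A reader might also take 1.11 to 1.17 as the expected size, but that range assumes every patient starts WBRT on the last permitted day. Nor do patients who merely worsen early drop out: anyone who completes WBRT stays in the set, even if they progress or die before the week 12 scan.

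**The effect may be small.** The synopsis goal is 56 treated, which means no difference if all 56 complete WBRT. Counts left in SAP Table 51 (49 + 9 and 43 + 15, each 58) suggest about 58 treated. If 56 of those were evaluable, the factor would be at most 1.036; if 50 were, 58/50 = 1.16. The evaluable number is unknown.

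**Part of the remedy is already there.** Exact two-sided 95% confidence intervals are specified in protocol 9.4.2.3, and Tables 34 to 36 have a row for patients not evaluated within the total. Both rates are secondary and descriptive, with no decision rule, and the primary conclusion is unaffected. All of this is correct and limits the weight of the point.

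**Conclusion.** The mismatch is established from the text: the protocol defines BORR and DCR over treated patients, and SAP Tables 34 to 36 present them over evaluable patients while restating the treated-patient definition. Upward bias is the likely direction, because treated patients who die before completing WBRT are failures that the evaluable set removes. It is not certain, because patients who stop WBRT for other reasons could move the rates either way.

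The multiplier is 1.00 if no treated patient is excluded, about 1.04 to 1.06 with the earliest WBRT start, and 1.11 to 1.17 with the latest. The figures above 1.00 rest on a constant hazard, on 1-year survival of 20% to 35%, and on deaths being the only exclusions. The eligibility criteria rule out patients in rapid deterioration, which may make early deaths fewer than the model implies. The point deserves correction as a matter of secondary-endpoint reporting; it does not threaten the primary analysis.

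**What to change.** Run SAP Tables 34 to 36 on all treated patients. State that patients not evaluated stay in the denominator and count as non-response for BORR and as no disease control for DCR. Report the exact 95% confidence intervals already specified in protocol 9.4.2.3. Keep the evaluable-set versions as a sensitivity analysis labelled as such, and give the number of treated but non-evaluable patients with the reason for each.

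If the sponsor prefers the evaluable set as the main population for response, the protocol definitions and the SAP's restatement of them should be amended and the choice justified.

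The cost is a few extra tables and rates that may be slightly less favourable. No new data collection is needed, since the 12-week assessment is already asked of everyone who enters treatment.

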9.3.2.3 Disease Control Rate (DCR)

DCR is as the total number of treated subjects in each population subset with BOR of CR, PR or SD, divided by the total number of treated subjects in the subset.

9.3.2.4 Duration of Response

A subject's duration of response is defined as the time between the date measurement criteria are first met for overall response of PR or CR (whichever status is recorded first, and if subsequently confirmed) and the date of disease progression or death, whichever occurs first. For subjects who undergo tumor resection on study, duration of response will be censored on the date of last tumor assessment prior to resection. For those subjects who remain alive and have not progressed, duration of response will be censored on the date of last tumor assessment.

9.3.2.5 Duration of Stable Disease

Duration of stable disease is defined for subjects whose BOR is SD as the time between when SD is first documented and the date of PD or death (whichever occurs first). For a subject who undergoes tumor resection following Week 12 but prior to disease progression, duration of stable disease will be censored on the date of the last evaluable tumor assessment prior to resection. For subjects who have BOR of SD at Week 12, the date of PD following thereafter (where available) will be used in the analysis of duration of stable disease. For subjects with BOR of SD who have not subsequently progressed and who remain alive, duration of stable disease will be censored on the date of last evaluable tumor assessment.

9.4 Analyses

9.4.1 Demographics and Baseline Characteristics

Demographic and baseline laboratory results will be summarized by population subset using descriptive statistics.

9.4.2 Efficacy Analyses

9.4.2.1 *Methods for Time to Event Primary Endpoint*

The yearly rate of survivors will be the actual proportion of patients alive after 1 year of the first administration of ipilimumab.

9.4.2.2 *Methods for Time to Event Secondary Endpoints*

The overall survival and event-free survival probabilities will be estimated and plotted using the Kaplan-Meier product-limit method.

Additionally, 1 and 2 year rates will be also based upon Kaplan-Meier estimates along with their corresponding log-log transformed 95% confidence intervals.

The progression-free survival probabilities will also be estimated and plotted using the Kaplan-Meier product-limit method. Duration of response, duration of stable disease, and overall survival in subjects with brain metastasis will also be described using these same Kaplan-Meier methods.

A differential analysis will be done with intracranial and extracranial disease.

9.4.2.3 *Methods for Proportion Based Rates Secondary Endpoints*

For BORR and DCR, descriptive summary statistics (e.g., total number of patients, number and percent responders, 95% confidence interval) will be used. An exact two-sided 95% CI for these rates will be computed. A differential analysis will be done with intracranial and extracranial disease.

9.4.3 Safety Analyses

Descriptive statistics of safety will be presented for all treated subjects using the National Cancer Institute (NCI) Common Terminology Criteria for Adverse Events (CTCAE) version 4.0. All on-study AEs, drug-related AEs, immune-related AEs, SAEs, and drug-related SAEs will be tabulated using worst grade

per NCI CTCAE v4.0 criteria by system organ class and by preferred term. The listings by subject will be produced for all deaths, all SAEs, and all AEs leading to discontinuation of study drug. On-study laboratory parameters, including hematology, serum chemistry, liver function, and renal function will be summarized using worst grade per NCI CTCAE v4.0 criteria. The reporting period for safety data will be from the first dose of study medication to 90 days (> 5 half lives) after the last dose is received.

Immune-related Adverse Events (irAEs)

Immune-related adverse events (irAEs) are AEs of unknown etiology, which are consistent with an immune phenomenon and identified by the investigator as study treatment related. The irAEs will be defined using a predefined list of MedDRA highlevel group terms, high-level terms and preferred terms; changes may be made to this list with each new version of MedDRA. Six (6) subcategories of irAEs will be reported: GI, liver, skin, endocrine, neurological, and other. Immune-related AE summaries will also be produced on diarrhea as a separate grouped term. Analysis of irAEs will be based on all treated subjects who received at least one dose of study therapy, and the reporting period will be from the first dose of after the last dose is received.

Immune-mediated Adverse Reactions (imARs)

This study will also describe immune-mediated adverse reactions (imARs) using the same adjudication algorithm and predefined list of AEs of special interest (enterocolitis, hepatitis, dermatitis, endocrinopathies, neuropathies, and other) used for the USPI. Specifically, the determination of imAR will take into account available clinical evidence through ruling out non-inflammatory etiologies such as infection or tumor progression, and consideration of evidence of inflammation such as tumor biopsies or responsiveness to steroids, but not the causality assessment of the investigator. imARs are likely to be

inflammatory events associated with ipilimumab treatment. Documentation of surveillance, intervention and outcomes are to be documented in the CRFs for inclusion of the imAR assessment. Analysis of imARs will be based on all treated subjects who received at least one dose of ipilimumab. The reporting period will be from the first dose of study therapy to 90 days after the last dose is received.

9.4.5 Exploratory Analyses

Two types of ALC analyses will be done: pharmacodynamic and predictive. Both analyses will include all treated subjects with known date of first dose of ipilimumab. Pharmacodynamic analyses will examine the patterns of change in ALC over time, and how these patterns might differ between treatment arms. Predictive analyses will examine potential relationships between ALC and measures of response such as overall survival.

The proposed biomarker study includes analysis of tumor tissue at diagnosis and serum/peripheral blood at different phases within the treatment schedule. All analysed parameters will be correlated with progression-free survival (PFS), overall survival and histopathological parameters.

For the statistical analysis, it will be used binary variables, reflecting the positivity status of the measures (yes or no; presence/absence). Association with histopathological parameters. The significance level will be set at 5%. To study the impact of the histological, immunohistochemical and molecular factors on progression-free survival (PFS) and overall survival (OS), the Kaplan-Meier proportional risk test (log rank) will be used. Evidence of the relative risk for each patient will be also provided by means of a Cox proportional hazards model using stepwise selection to identify the independent predictors of poor outcome.

For the kinetic profile of the serum/blood biomarkers, each variable will be considered as continuous. A correlation at different points of the treatment schedule will be considered and the slope value will be used in order to distinguish those cases with no change, negative or positive trend. The threshold will be calculated after considering the behavior of the whole series.

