- In addition, in all ipilimumab trials examined to date, mean Absolute Lymphocyte Count (ALC) increased after ipilimumab treatment throughout the 12-week induction-dosing period, in a dose-dependent manner. In an analysis of ipilimumab at 0.3, 3, or 10 mg/kg in melanoma studies CA184007, CA184008, and CA184022 combined, the rate of change in ALC after ipilimumab treatment was significantly associated with dose (p = 0.0003), with the largest rate at 10 mg/kg ipilimumab. Moreover, the rate of change in ALC over the first half of the induction-dosing period was significantly associated with clinical activity in these studies (p = 0.009), where clinical activity was defined as CR, PR, or prolonged SD (ie, SD lasting at least 6 months from first dose). Although these analyses alone could not determine whether the rate of change in ALC was specifically associated with clinical activity in response to ipilimumab treatment, as opposed to being generally prognostic, these results do suggest a potential benefit to higher rates of ALC increase after ipilimumab treatment. Among the 3 doses evaluated, 10 mg/kg ipilimumab led to the greatest such rates.
- In the 3 primary studies conducted in advanced melanoma (CA184007, CA184008, and CA184022), subjects treated with 10 mg/kg during the induction period had the highest response, disease control rates, median OS as well as 1-year and 2-year survival rates compared to other doses. The CA184022 data are summarized in Table 10.

Table 10: Summary of Phase 2 Response Data in Melanoma (CA184022)

	10 mg/kg (n = 72)	3 mg/kg (n = 72)	0.3 mg/kg (n = 73)
BORR (mWHO) – %	11.1	4.2	0
(95% CI)	(4.9 - 20.7)	(0.9 - 11.7)	(0.0 - 4.9)
DCR (mWHO) – %	29.2	26.4	13.7
(95% CI)	(19.0 - 41.1)	(16.7 - 38.1)	(6.8 - 23.8)
Survival rate at 1 year - %	48.64	39.32	39.58
% , 95% CI	(36.84, 60.36)	(27.97, 50.87)	(28.20, 51.19)

GRAY-B Study (GEM 1202). V1.0 (28 Nov 2013)

Survival rate at 2 year - %	29.81	24.20	18.43
%, 95% CI	(19.13, 41.14)	(14.42, 34.75)	(9.62, 28.22)
Overall median survival	11.43	8.74	8.57
95%CI (months)	(6.90, 16.10)	(6.87, 12.12)	(7.69, 12.71)

Finally, the dose and schedule in study CA184156 is the one that was evaluated in the signal finding study CA184041, with an acceptable safety profile and improvement of irPFS and OS.

Treatment with ipilimumab has demonstrated clinically important and durable tumor responses in several malignancies including melanoma, prostate cancer, and renal cell carcinoma.

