2.2 Secondary Objectives

- Efficacy – Endpoints:
 - Progression-Free survival-PFS (median, 6-month PFS rate)
 - Intracranial PFS (median, 6-month PFS rate)
 - Extracranial PFS (median, 6-month PFS rate)
 - Overall survival (median)
 - Response rate: (global, intracranial, extracranial) (“Immune-related response criteria”)
- Safety: Adverse Event rates
- Feasibility: dose delays/reductions, treatment exposure

2.3. Exploratory Objectives.

- Potential baseline predictors of efficacy (in tumour tissue and peripheral blood – see 6.4.3.)
- Potential early surrogates for response: inpatient variation of quantitative apparent diffusion coefficients of serial diffusion-weighted magnetic resonance imaging

⁶⁸ Hodi FS, O'Day SJ, McDermott DF, et al. Improved survival with ipilimumab in patients with metastatic melanoma. *N Engl J Med.* 2010 Aug 19;363(8):711-23.

⁶⁹ http://www.ema.europa.eu/docs/en_GB/document_library/EPAR_-_Product_Information/human/002213/WC500109299.pdf

3 **STUDY DESIGN**

This is a non-controlled, single stage, multicenter phase 2 clinical study. A total of 56 evaluable patients will be treated in this study.

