The aim of this optional study is to determine whether a correlation between the proposed biomarkers and disease behavior (progression, overall survival, treatment response) exist in patients with melanoma metastatic to the brain, that have specifically consented for the participation in this part of the study.

The present biomarker plan proposes assessment of such biomarkers to investigate their associations with immune-mediated adverse events when ipilimumab is administered with radiation therapy:

- To evaluate tumor biomarkers pathways by IHC and their correlation with prognosis as well as their role as predictive factors to treatment with ipilimumab+radiotherapy in 29 patients participating on GEM 12-02 clinical trial.
- To evaluate serum levels of several cytoquines (by means of cytoquines panel) at baseline, and before each ipilimumab administration (expected 4-5 samples per patient, 29 patients).
- To evaluate Peripheral Blood Mononuclear Cells (PBMCs), with true counts for absolute numbers and percentage at baseline, and before each ipilimumab administration (expected 4-5 samples per patient, 29 patients).

6.4.3.b Biomarker Measures

- ALC will be assessed as a part of standard hematology panel.
- CRP will be obtained as a component of the serum chemistry lab test.
- Tumor Samples: at least 29 tumor samples (biopsies) will be collected and histology and IHC will be carried out to evaluate a panel of biomarkers that includes: CD3, CD4, CD8, CD31, PD-1, PD-L1, CD45RO, CD68, NK, DC, CD80, CD86, ICAM, VCAM, HLA-A,B,C, HLA-DR, PTEN.
- Serum Samples will be evaluated in at least 29 patients at 4-5 timepoints (116 refrigerated serum samples). For each sample, 10 ml of serum will be collected and a cytokine panel will be carried out, including:

Cytokines			
IFN- γ	TNF- α	IL-1 β	IL-2
IL-4	IL-6	IL-7	IL-8

IL-10	IL-12	IL-15	IL-17
Adhesion molecules			
sICAM-1	sVCAM-1	sCD25	

- Peripheral Blood immune cells will be evaluated in at least 29 patients at 4-5 timepoints (116 refrigerated peripheral blood samples). For each sample, 10 ml of heparin blood will be collected for flow cytometry to evaluate a panel of cells that include:

T cells			
CD3	CD4	CD8	CD56
CD45RA	CD45RO	CD62L	LFA-1 (activated conformation)
NK cells			
NKp46	CD16	CD56	
T reg			
CD4	CD25	FoxP3	
MDSC			
CD14	CD15	CD33	HLA-DR
DC			
BDCA-1	BDCA-2	BDCA-3	
T cell activation (with PMA + ionomycin)			
CD69	CD25	IFN-	IL-4
IL-17	LFA-1(active conformation)		

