9. STATISTICAL METHODOLOGY

9.1. Sample size.

The primary endpoint in this study is the 1-year actual survival rate. A one-stage Fleming design has been adopted. Assuming a historical 1-year survival rate of 20% (with radiation therapy + best supportive care) for the selected population, a sample size of 56 evaluable patients would be needed to show that the addition of ipilimumab to radiotherapy generates a 1-year survival rate of 35%, reaching 80% power at the 0.05 significance level.

A total of 56 evaluable patients would need to be included. In case that at least 17 out of these 56 evaluable patients would survive for at least one year, the conclusion of the trial would be that the higher 1-year survival rate of 35% is more likely for the combination than the historical 20% survival rate.

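### The biomarker analyses labelled 'predictive' come from a single treated arm, so they estimate association with outcome on treatment and cannot separate prognosis from modification of ipilimumab benefit

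*Protocol*

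**What the plan says.** Protocol section 3 describes the design: "This is a non-controlled, single stage, multicenter phase 2 clinical study". It adds: "A total of 56 evaluable patients will be treated in this study". All treated patients receive ipilimumab, and whole-brain radiotherapy is planned for all.

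Three parts of the protocol bear on the markers.

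- **Section 6.4.3.a** names correlation of the immunohistochemical markers with prognosis and, alongside it, "their role as predictive factors to treatment with ipilimumab+radiotherapy in 29 patients". Prediction is thus an aim in its own right and not a loose synonym for prognosis. The same section says predictive markers can serve to stratify patients and to support decisions about stopping treatment.
- **Section 9.4.5** divides the ALC work into pharmacodynamic and predictive parts, both in all treated patients. Of the second it says: "Predictive analyses will examine potential relationships between ALC and measures of response such as overall survival". No test is named for it. For histological, immunohistochemical and molecular factors it plans log-rank tests and a stepwise Cox model on progression-free and overall survival, at 5%. It also asks how ALC patterns differ across arms, although there is only one.
- **Section 1.3.5.d**, on earlier ALC data pooled over three ipilimumab doses, says those analyses could not settle whether the change in ALC was "specifically associated with clinical activity in response to ipilimumab treatment, as opposed to being generally prognostic".

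SAP section 1.5.1.1 relates baseline characteristics, including CRP, neutrophil/lymphocyte ratio, Karnofsky status and single or multiple brain metastases, to 1-year survival. It calls this possible association. It does not cover ALC on its own or the tissue and cytokine panels.

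**The concern.** A predictive marker is one for which the effect of treatment differs by marker level. Testing that requires outcome by marker level both with and without the treatment. The planned analyses compare outcome by marker level among patients who all receive the treatment, so their null hypothesis is that the marker is unrelated to outcome on treatment. A marker that only reflects disease burden or general condition can reject that null.

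Two misreadings are possible. A prognostic marker may be reported as identifying patients who benefit from adding ipilimumab. Conversely, a marker that does modify benefit may show nothing because its prognostic effect runs the other way. The uses named in section 6.4.3.a, stratification and support for stopping decisions, are where the first misreading would matter.

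**Working it through.** **1. The plan's own figure.** The only error rates stated are for the primary endpoint. The null 1-year survival is 20%, and the design assumes that the combination "generates a 1-year survival rate of 35%, reaching 80% power at the 0.05 significance level". The success rule begins: "In case that at least 17 out of these 56 evaluable patients would survive for at least one year". By exact binomial:

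- P(X ≥ 17 | n = 56, p = 0.20) = 0.0432
- P(X ≥ 17 | n = 56, p = 0.35) = 0.806

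The design reproduces at a one-sided 0.05 level, and nothing below affects it. The documents give no power or error rate for the biomarker analyses.

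**2. What a single arm estimates.** Let M be the marker and T = 1 if ipilimumab is given:

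log h(t) = log h₀(t) + βM + γT + δMT

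Here β is the prognostic effect and δ the predictive one. With T = 1 for everyone,

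log h(t) = [log h₀(t) + γ] + (β + δ)M

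Only β + δ can be estimated. If δ = 0 and β ≠ 0, the test has power against a purely prognostic marker. If the prognostic hazard ratio is 1.5 and the modification ratio is 1/1.5, the product is 1.0 and a truly predictive marker shows no association. A larger sample changes neither result.

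**3. How often a purely prognostic marker would be significant.** Inputs from the protocol:

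- 29 patients for the biomarker set (6.4.3.a; 6.4.3.b says at least 29), and about 56 treated for ALC (section 3; 9.4.5).
- Study closure 18 months after the last first dose, with at most 36 months per patient (section 3). Accrual from 03/2014 to 10/2015 (synopsis) is 19 months, so follow-up runs from 18 to 37 months, capped at 36.
- 1-year survival of 20% or 35% (9.1).

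Assumptions, because the documents give none of these: exponential survival, a 50/50 marker split, a two-sided test, and prognostic hazard ratios of 1.3, 1.5 and 2.0.

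Expected deaths are N × mean[1 − exp(−λf)], where f is follow-up in years and λ = −ln(0.35) = 1.05 or −ln(0.20) = 1.61 per year. For N = 29 this gives 26.1 or 28.1 deaths; for N = 56 it gives 50.3 or 54.2.

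Power (Schoenfeld) = Φ(|ln HR| × √(E·p(1−p)) − 1.96), with E deaths and a proportion p in one marker group. Example for E = 26, HR 1.5: 0.4055 × √6.5 = 1.034, and Φ(1.034 − 1.96) = 0.177.

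| Set | Deaths | Split | HR 1.3 | HR 1.5 | HR 2.0 |
|---|---|---|---|---|---|
| 29 patients | 26 | 50/50 | 9.8% | 17.7% | 42.4% |
| 29 patients | 28 | 50/50 | 10.3% | 18.7% | 45.0% |
| 29 patients | 26 | 30/70 | 8.9% | 15.6% | 36.7% |
| 56 patients | 50 | 50/50 | 15.1% | 29.9% | 68.8% |
| 56 patients | 54 | 50/50 | 16.0% | 31.9% | 72.1% |
| 56 patients | 50 | 30/70 | 13.4% | 25.9% | 61.3% |

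Log-rank simulation agrees. With 56 patients and 1-year survival of 35% it gave 15.4%, 30.4% and 68.1%. With 29 patients it gave about 18% at HR 1.5 and 42% at HR 2.0.

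With deaths up to 1 year only, the 29-patient set (19 to 23 deaths) gives 14–16% at HR 1.5 and 33–38% at HR 2.0. The 56-patient set (36 to 45 deaths) gives 23–27% and 55–64%.

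**4. Events available to a Cox model.** Section 6.4.3.b lists 17 immunohistochemical markers against about 26 deaths in 29 patients. A model with one marker, Karnofsky status and brain metastases has three coefficients: 26/3 ≈ 8.7 deaths per coefficient in the 29-patient set, and 50/3 ≈ 16.7 for ALC.

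**The case against.** The strongest reply is that nothing in the plan declares a marker predictive. The objectives are exploratory, no decision rule exists, the stepwise Cox model looks for predictors of poor outcome (which is prognostic language), and the SAP speaks only of association. This stands as far as it goes. A reader might infer from the table a false-positive rate far above 5%, but the documents do not support that: the percentages are ordinary power to detect a real survival association.

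A reader might also attach the 30–68% range to the planned log-rank and Cox tests. Those are specified for tissue and molecular factors, and the tissue panel is planned in 29 patients. The larger range would apply to ALC only if the same test were used there, and section 9.4.5 names none. Only the log-rank test was evaluated; no stepwise Cox model was simulated.

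The hazard ratios are assumptions. The nearest figure in the protocol is the melanoma prognostic score in section 1.2.1, where adjacent bands have medians of 4.7 and 8.8 months (8.8/4.7 ≈ 1.9 under exponential survival). That compares bands of a composite score, not levels of a single blood or tissue marker. Nor do the documents show that ALC, CRP or the cytokines are purely prognostic; section 1.3.5.d leaves the ALC question open.

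The exploratory label does not remove the problem. It limits how strongly a result may be claimed, not which quantity is estimated, and section 6.4.3.a still sets prediction as an aim that no planned analysis can meet. The caveat in section 1.3.5.d shows that the authors know the difficulty. There, even data from three doses did not resolve it; here there is one planned dose.

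**Conclusion.** The point holds as one of labelling and estimand. Sections 6.4.3.a and 9.4.5 present marker–outcome analyses in one treated group as informing predictive value, and the design has no comparator, external marker data or interaction test that could supply it. This conclusion follows from the design and needs no numerical assumption.

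The size is illustrative: about 10%, 18% and 42% for hazard ratios of 1.3, 1.5 and 2.0 in 29 patients, and about 15%, 30% and 68% in about 56. It rests on the assumed hazard ratios, an even split, near-complete follow-up and a two-sided 5% log-rank test. A 30/70 split or fewer deaths lowers it.

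A reader might infer that the trial will wrongly declare markers predictive at these rates, or that its main conclusion is at risk. Neither follows: there is no declaration rule, and the primary endpoint is untouched. The point is minor, but worth correcting before results are reported under the present label.

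**What to change.** In Protocol sections 6.4.3.a and 9.4.5:

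1. Replace 'predictive' with 'prognostic / associated with outcome on treatment', and state that no predictive claim will be made from this single-arm trial.
2. Delete the reference in 9.4.5 to ALC patterns differing by treatment arm.
3. Replace stepwise Cox selection with Cox models for one marker at a time, adjusted for Karnofsky status (70–80 vs 90–100) and brain metastases (single vs multiple). Section 1.2.1 reports Karnofsky status and number of brain metastases as the only significant factors in its 481-patient melanoma analysis, and SAP section 1.2 already tabulates both in these categories. The SAP split is coarser than the 1, 2–3 and >3 grouping of section 1.2.1.
4. State that adjustment shows association beyond known prognosis and does not turn an association into evidence of prediction.
5. If error rates or power are quoted, give them separately for the 29-patient set and for all treated patients, with their assumptions.

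The cost is a wording change and two covariates already planned for tabulation. The downside is a weaker label for the biomarker results and slightly wider intervals, mostly in the 29-patient set.
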